### 3. Study Treatment Arms

3.1 Test Arms

There will be a Primary Study Arm and a Secondary Study Arm in this study.

- Primary Study Arm – Hypothesis-driven analysis, TAAAs which are anatomically suitable for treatment with the TAMBE System and do not require proximal extension with a CTAG Device (N=102)
- Secondary Study Arm – Non hypothesis-driven analysis, TAAAs which are anatomically suitable for treatment with the TAMBE System and would require proximal extension with CTAG Device(s) (N=20 minimum, 100 maximum as aggregate total of all types). Subjects that undergo placement of the CTAG Device but do not complete the implant of the TAMBE Device whether by subject choice or Investigator discretion will only have their adverse events reported through 30 days after implant and withdrawn from the study.

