Brief Inclusion Criteria	
 
• Aortic aneurysm involving the visceral vessels requiring treatment defined as at least one of the following: 
 
○ Fusiform aneurysm diameter <math>\geq</math> 5 cm
 
○ Saccular aneurysm (no diameter requirement)
 
○ Rapid aneurysm growth (<math>\geq</math> 5 mm in one year)
 
 
 
• An Informed Consent Form signed by Subject or legal representative
 
• Appropriate aortic anatomy to receive the TAMBE Device defined as all of the following: 
 
○ For the TAMBE Aortic Component, proximal aortic landing zone diameters between 22 -34 mm
 
○ Proximal seal zone <math>\geq</math> 20 mm in length
 
 
 

Brief Exclusion Criteria	
 
• Prior open, aortic surgery of the ascending aorta or aortic arch
 
• Myocardial infarction or stroke within 1 year of treatment (staged or index procedure)
 
• Previous instance of Heparin Induced Thrombocytopenia type 2 (HIT-2) or known hypersensitivity to heparin
 
• Renal insufficiency (creatinine value <math>></math> 1.8 mg/dL, GFR <math><</math> 30, or patient undergoing dialysis)
 

Expected Time to Complete Enrollment	
Primary Study Arm Subject Accrual: 27-32 months
 
Follow-up – 5 years from last subject enrollment

Brief Schedule of Events	
Screening
 
Pre-Treatment
 
Treatment
 
Discharge
 
Follow-up (30 day, 3, 6, 12 months and annually thru 5 years)

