## 5. Statistical Analyses

### 5.1 Analysis Populations

The following populations will be used in various analyses of the data collected in the AAA 17-01 study:

1. All Enrolled Subjects - This population will consist of all enrolled Subjects. A patient is considered enrolled into the study once the Main informed consent has been signed and dated.
2. All Enrolled and Implanted Subjects - This population will consist of all enrolled and implanted Subjects. A patient is considered enrolled into the study once the Main informed consent has been signed and dated, and successfully implanted with the study device (TAMBE in the primary arm, CTAG + TAMBE in the secondary arm).
3. Uncomplicated Technical Success Eligible Population (each study arm) [Per protocol population] - This population will consist of enrolled and implanted Subjects with a follow-up visit at or after 30 days following initial TAMBE Device implant procedure. Additionally, any Subjects with an eligible technical success event, as defined in **Section 2.3.1**, even if they did not complete a follow-up visit at or after 30 days following initial procedure, will be included.
4. Clinically Significant Reintervention / Lesion Related Mortality Population (each study arm) - This population will consist of enrolled and implanted Subjects that have completed the 12 month analysis window. Additionally, any Subjects with an eligible clinically significant reintervention event, as defined in **Section 2.3.1**, even if they did not complete the necessary follow-up visit or imaging to otherwise be included in the population, will be included.
5. Secondary Effectiveness Populations (each study arm, each endpoint) - These populations will consist of enrolled Subjects with an evaluable result for the specific variable.
6. Reduced Profile VBX Population – This population will consist of the subjects in the Continued Access Phase who had been implanted with at least one reduced profile VBX device.

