#### 5.4 Statistical Analysis of Endpoints

One-sided exact Clopper-Pearson confidence intervals for binomial proportions ( $\alpha=0.05$ ) will be constructed to test the Uncomplicated Technical Success and Clinically Significant Reintervention hypotheses in the Primary Study Arm. The null hypothesis for each endpoint will be rejected if the lower bounds of the 95% confidence interval exceeds the corresponding performance goal. This is equivalent to stating that the estimated effectiveness and safety must exceed the PG with a Type I error rate ( $\alpha$ ) of  $< 0.05$ .

Primary and Secondary Endpoints will be summarized in the Secondary Study Arm, but no hypotheses tests will be performed.

All events must meet the protocol definition.

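### Secondary Arm subjects who receive CTAG but not TAMBE fall outside both co-primary populations, while the event-counting rules include all enrolled subjects, so the arm's co-primary summaries are ambiguous and can be conditional on completing staging

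*Combined protocol and SAP*

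**What the plan says.** There is one combined document; section numbers are those of the SAP.

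- **Section 3.1** sets the Secondary Arm at "N=20 minimum, 100 maximum as aggregate total of all types". Subjects who have CTAG placed but do not complete TAMBE, "whether by subject choice or Investigator discretion", "will only have their adverse events reported through 30 days after implant and withdrawn from the study".
- **Section 5.1, Population 2** takes implanted to mean "successfully implanted with the study device (TAMBE in the primary arm, CTAG + TAMBE in the secondary arm".
- **Section 5.1, Population 3** (first co-primary endpoint, each arm) consists of "enrolled and implanted Subjects with a follow-up visit at or after 30 days following initial TAMBE Device implant procedure". Population 4 (second co-primary endpoint, each arm) also starts from enrolled and implanted subjects and asks for the 12-month window. Both then add subjects who had an event but lack the follow-up.
- **Section 5.1, Population 5** (secondary endpoints, each arm) asks only for an enrolled subject with an evaluable result.
- **Sections 5.4.1 and 5.4.2** count co-primary events in each arm among all enrolled subjects. Under section 5.1, enrolment is signature of the main consent.
- **Section 5.4**: "Primary and Secondary Endpoints will be summarized in the Secondary Study Arm", without hypothesis tests. It also requires every event to meet the protocol definition.
- **Table 1** evaluates technical success at the TAMBE index procedure. It times paraplegia, paraparesis, renal failure and stroke from the index endovascular procedure. **Table 3** lists the duration and hospital stay of the stage procedure separately.

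**The concern.** Section 2.1.1 says that this arm is to characterise device performance, with CTAG extension, for possible later use in Type I-III aneurysms. The documents treat a stage procedure as distinct from the index procedure, and section 3.1 foresees subjects who get CTAG and stop there. If such a subject stops because of a serious event at or after the first stage, that event bears directly on how the combined treatment performs.

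A co-primary summary restricted to subjects with both devices describes those who came through staging well enough to continue. That selection can make the combined treatment look safer and more deliverable than it is. A second problem is practical: the population rules and the event rules give different answers for the same subject, so two analysts could report different results from the same data.

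**Working it through.** The plan gives no power, performance goal or expected rate for this arm, so there is no stated figure to reproduce. The check is a comparison of rules, followed by an illustration.

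**Step 1. Follow one CTAG-only subject through each rule.**

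| Rule | Does the subject count? |
|---|---|
| Population 2 (5.1) | No; both devices are required |
| Population 3, base rule | No; not implanted, and there is no TAMBE date from which to count 30 days |
| Population 4, base rule | No; not implanted |
| Event add-back in Populations 3 and 4 | Unclear; it excuses missing visits or imaging and does not clearly waive the implant requirement |
| 5.4.1 and 5.4.2, event count | Yes, if an event meets the definition; enrolment is enough |
| Population 5 | Yes, where the variable is evaluable |
| 3.1, adverse events | Yes, through 30 days, then withdrawn |

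**Step 2. Time origin.** Even where 5.4.1 admits the subject, most Table 1 components need an index procedure. A subject with a stage procedure and no TAMBE procedure has no clear index date, so a first-stage stroke or paraplegia may not meet the definition as written. Lesion-related mortality is broader: it also takes in deaths related to the treated pathology or the graft, so a death between stages could qualify.

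**Step 3. Effect of the conflict.** The documents give no non-completion rate. Assume the minimum of 20 completers with no procedural safety event, and k CTAG-only subjects who each stopped because of one.

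- Population 3 for numerator and denominator: 0/20 = 0%.
- Numerator from 5.4.1, denominator from Population 3: k/20, that is 1/20 = 5.0% or 2/20 = 10.0%. Here the numerator holds subjects who are not in the denominator.
- All subjects who started staging: k/(20 + k), that is 1/21 = 4.8% or 2/22 = 9.1%.

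The one-sided exact 95% upper limit is the p that solves Σ(i = 0 to x) C(n,i) pⁱ(1 − p)ⁿ⁻ⁱ = 0.05.

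| x/n | Rate | Upper limit |
|---|---|---|
| 0/20 | 0% | 1 − 0.05^(1/20) = 13.9% |
| 1/21 | 4.8% | 20.7% |
| 2/22 | 9.1% | 25.9% |

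**Step 4. Technical success, worst case.** Assume 18 or 16 successes in 20 completers and count every non-completer as a failure, so the rate is x/(20 + k).

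| Completers | k = 1 | k = 2 |
|---|---|---|
| 18/20 = 90.0% | 18/21 = 85.7% | 18/22 = 81.8% |
| 16/20 = 80.0% | 16/21 = 76.2% | 16/22 = 72.7% |

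These are bounds, because not every non-completion is a device failure. With 100 completers, the same proportional shift needs about five times as many non-completers: 90/105 = 85.7% at k = 5.

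**The case against.** Much of the case on the other side stands.

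- A reader might infer that CTAG-only subjects are excluded from every endpoint of the arm. The documents do not support that. Population 5 does not require implant, and the secondary endpoints include aneurysm-related mortality, the individual procedural safety elements and the stage-procedure measures.
- A reader might infer that first-stage events vanish from the results. They do not: adverse events are reported through 30 days, and section 6 has the DSMB review a summary of all reported adverse events. What can be lost is their place in the co-primary composites, and events after day 30.
- A reader might conclude that no analysis of these subjects is planned. The table of contents lists section 5.6.2.3 on subjects enrolled but not implanted, and its text is redacted. It may partly cover them. It stands among the additional analyses, however, and nothing visible suggests that it changes Populations 3 and 4 or resolves the conflict with 5.4.1 and 5.4.2.
- The exclusion "Myocardial infarction or stroke within 1 year of treatment (staged or index procedure") might be read as a route by which a first-stage stroke removes a subject. That is speculation: nothing visible says that eligibility is rechecked between stages, and the wording may only fix the look-back period.
- Section 3.1 names only choice and discretion as reasons for non-completion. It does not say that a death or disabling event between stages falls under the rule; the visible text is silent on this.
- Counting a subject who simply declines TAMBE as a technical failure does not follow from Table 1, which concerns delivery, deployment and withdrawal of the devices.

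**Conclusion.** The point holds in this limited form. Under section 5.1, CTAG-only subjects are outside both co-primary base populations; section 3.1 stops their reporting at 30 days; and sections 5.4.1 and 5.4.2 count events in a wider group than the denominators contain. If the section 5.1 populations govern, the Secondary Arm's co-primary summaries are conditional on completing staging and can omit the events that prevented it.

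The size cannot be derived from the documents. The move from an upper limit of 13.9% to 20.7% or 25.9% rests on assumed counts: 20 completers without an event, and one or two non-completers who each had one. That choice maximises the contrast. It does show that at the 20-subject minimum, one or two people change the picture.

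A reader might also infer that the trial's conclusions are at risk. They are not: the arm is descriptive, section 5.3 bases inference for the marketing application on the initial 102 Primary Arm subjects, and no test, alpha, power or success criterion is touched. This should be corrected for the arm's reporting.

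**What to change.** 1. Reconcile sections 3.1, 5.1, 5.4.1 and 5.4.2. State whether a CTAG-only subject is in the numerator, the denominator, both or neither of each co-primary summary, whether the event add-back waives the implant requirement, and how a death or disabling event between stages is classified. If section 5.6.2.3 already does this, refer to it from section 5.4.
2. Add to section 5.4 a descriptive summary of all Secondary Arm subjects in whom the first CTAG stage was started. Give the number of non-completions with the reason for each, and deaths and events of the procedural safety type from the first stage up to withdrawal. Place it beside the completer results, which stay as they are.
3. Show technical success with non-completers counted as failures only as a labelled worst case.

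The cost is one extra descriptive table and possibly less favourable arm results. There are two limits on the data. Disabling stroke needs a modified Rankin score at 90 days, so it may not be fully classifiable after withdrawal. The visible text also does not show that the reason for non-completion is collected, which should be confirmed.

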3.2 Control Arm(s)

There are no control arms in this study.

4. Study Data Collection

Subjects will be evaluated, at a minimum, using the schedule of events described in Table 4. The timing of study evaluations will be done according to the schedule defined in Table 5. Investigators will be held responsible for the performance of all Protocol-required testing at their respective time points, including testing done at institutions different than the implanting study site. It is highly recommended that subjects return back to their centers of enrollment for follow-up evaluations to foster testing compliance and continuity of care.

Sites are to schedule all study testing to be performed within the ideal visit window; however, any available data collected in the analysis window will be summarized as occurring within the given window. Data collected outside the ideal window, but within the analysis window will not be considered a protocol deviation.

4.1 Study Collection Intervals

Subjects will be asked to return for follow-up visits at one (1), three (3), six (6), 12, 24, 36, 48, and 60 months post-treatment. At each follow-up visit, subjects will undergo an evaluation for adverse events.

Table 4: Schedule of Events

	Pre-treatment (Screening)	Treatment	Hospital Discharge	One Month	Three Months	Six Months	Annually through 5 Years
Informed Consent	X						
Demographics and Medical History	X						
Risk Scales (ASA, NYHA, SVS)	X						
Physical examination	X		X	X	X	X	X
Adverse Events	X	X	X	X	X	X	X
Medication Review	X		X	X	X	X	X
Modified Rankin Scale a,b	X		X	X	X if applicable	X	
Spinal Cord Ischemia Scale a	X		X	X		X	

NIH Stroke Scale c	X		X If applicable				
SF-36 Questionnaire	X			X	X	X	X
Serum Creatinine Concentration	X		X	X	X	X	X
Spiral CTA (contrast) d	X			X		X	X
Spiral CT (non-contrast)				X		X Optional	X Optional
Completion Angiogram		X					
Magnified Branch Visualization		X					
Abdominal Ultrasound	X		X	X	X	X	X
Multiplanar Device Radiographs (X Ray)				X		X	X

a If subject is unable to return to the site for a follow-up visit, they may be contacted by telephone to evaluate the Modified Rankin Scale and Spinal Cord Ischemia Scale.

b For subjects suspected of having a stroke event within 30 days following the index endovascular procedure an additional mRS score should be completed at 90 days following the suspected stroke event but no greater than 120 days post index endovascular procedure.

c NIH Stroke Scale should be performed for any subject suspected of having a stroke event that undergoes the treating site's stroke protocol during the study interval from the initiation of the index endovascular procedure until discharge. The scale should be performed as soon as possible after learning of the suspected event and again at the time of discharge.

d CTA of chest/abdomen/pelvis at Screening. CTA of abdomen and pelvis at all follow-up visits, except for Secondary Study Arm Subjects who must have a CTA of chest/abdomen/pelvis at all visits. MRA may be used in place of CTA during follow-up if the Subject is contraindicated for CTA.

#### 4.2 Follow-up Visit Windows

Follow-up visits will be scheduled at appointed times after the date of treatment. The Sponsor recognizes that Subjects may not be able to return for follow-up visits on the exact date required. Thus, a period during which each visit is allowed is demonstrated in **Table 5**.

**Table 5: Follow-up Visit Ideal and Analysis Window Definitions**

Follow-up Visit	Ideal Window (days)	Analysis Window (days)
Procedure	0	0
Discharge*	Before hospital discharge	N / A
Post-Procedure	Not required	1-14
1 Month	23-44	15-59
3 Month	76-104	60-126
6 Months	150-210	127-242
12 Months	275-455	243-546
24 Months	640-820	547-911
36 Months	1005-1185	912-1275
48 Months	1370-1550	1276-1640
60 Months	1735-1915	1641-2006

\*Follow-up visit is categorized as "Discharge" through initial hospitalization, regardless of length.

#### 4.3 Data and Safety Monitoring Board

See Section 9.3 of the protocol for information on the Data and Safety Monitoring Board.

#### 4.4 Clinical Event Committee

See Section 9.4 of the protocol for information on the Clinical Events Committee.

#### 4.5 Site Enrollment Restrictions

The maximum number of implanted subjects that may be implanted at a single site is as follows:

- Primary Study Arm Subjects: 15 subjects
  - Continued Access + Primary Study Arm: 21 subjects (this is a temporary site maximum which will be lifted after the first 27 subjects have enrolled in Continued Access)
- Secondary Study Arm Subjects: No maximum

#### 4.6 Core Lab

See Section 6.4 of the protocol for information on the Core Lab.

#### 4.7 Handling of Missing Dates

Imputation of dates is not planned for Primary Analysis. However, if it becomes necessary for an analysis of adverse events, the earliest possible date will be used, given the information available. If the month and year are provided, but the day is missing, then the first day of the month will be imputed. If only the year is provided, then the first day of the first month will be imputed, or the first day after procedure imputed if the first day of the year is prior to the procedure.

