## 2. Study Design Overview

This will be a prospective, non-randomized, two-armed, multicenter study conducted at up to forty-five (45) Clinical Investigative Sites (referred to as “sites” in the remainder of this document) in the United States and Europe. A minimum of 122 subjects, up to a potential maximum of 202 subjects, will be implanted with the TAMBE Device across two independent study arms as described below.

- Primary Study Arm – Hypothesis-driven analysis, Thoracoabdominal aneurysms (TAAAs) which are anatomically suitable for treatment with the TAMBE Device and do not require proximal extension with a CTAG Device (N=102). This arm will be limited to pararenal aortic aneurysm and adapted Crawford Type IV TAAAs.
- Secondary Study Arm – Non hypothesis-driven analysis, TAAAs which are anatomically suitable for treatment with the TAMBE Device and would require proximal extension with CTAG Device(s). This arm will include adapted Crawford Type I-III TAAAs. (N=20-100 Subjects)

Up to 65 additional subjects may be implanted in the Continued Access Phase under the Primary Study Arm only. All sites will be allowed to enroll in the Continued Access Phase, and all sites and subjects will be treated and followed in the same manner as the Core Clinical Investigation.

- The reduced profile VBX Device cohort (a subset of the Continued Access phase) will follow the TAMBE protocol: all primary, secondary, and other endpoints will be collected for these subjects as per protocol in the same manner as for the other cohorts. The Target Vessel Technical Success of the reduced profile VBX Device for each vessel will also be assessed.
- To assess the compatibility of reduced profile VBX Device as a side branch component in conjunction with the TAMBE Aortic Component (AC), the following endpoints will be summarized at a subject level:
  - Uncomplicated Technical Success at Index Procedure
  - Procedural Safety data through 30-day follow-up
  - Summary of AEs through 30-day follow-up including Type Ic and IIc Endoleaks

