**Table 3: Secondary Endpoint Definitions**

Outcome	Definition	Endpoint Time Evaluated	Final Source Data
Standard Procedure / Hospitalization Metrics			
Aneurysm-related mortality	Defined as all deaths during hospitalization for index endovascular procedure and within 30 days of the index endovascular procedure or any secondary procedures due to the treated pathology, or the effectiveness of the endovascular repair (e.g., procedures to treat retrograde dissections, losses of patency, losses of device integrity, endoleaks, migrations,	30 Days	CEC

Outcome	Definition	Endpoint Time Evaluated	Final Source Data
	aortic expansions, aortic ruptures) and any deaths related to the treated pathology or endovascular graft (e.g., aneurysm rupture, retrograde dissection leading to fatal cardiac tamponade), unless evidence is available to demonstrate that the death is not lesion related.		
Individual elements of Procedural Safety 
 
• Aortic Rupture
 
• Lesion-related mortality
 
• Permanent paraplegia
 
• Permanent paraparesis
 
• New onset renal failure requiring dialysis
 
• Severe bowel ischemia
 
• Disabling stroke
 
	Reference Table 1 for definitions for these elements	Reference Table 1	Reference Table 1
Procedural blood loss	Estimated Blood Loss during Index Procedure (mm)*	Index Procedure	Site
Access-related complications	An Adverse Event determined by Site to be related to vascular access*	30 Days	Site
Procedural time	Duration of Index Procedure (minutes) [the time of incision will indicate the start time and the finish time is the time of closure ]. *	Index Procedure	Site
Stage Procedure Time	Duration of Stage Procedure (minutes) [the time of incision will indicate the start time and the finish time is the time of closure ]. *	Stage Procedure	Site
Length of hospital stay	Number of Days Subject stayed in hospital (from admission date to discharge date). *	Initial Hospitalization of Index Procedure	Site
Stage procedure length of hospital stay	Number of Days Subject stayed in hospital for stage procedure (from admission date to discharge date). *	Stage Procedure	Site
Extended Technical Clinical Success	Subjects who present within the 30-Day follow-up with no Type I or Type III endoleak, as evaluated by CTA, and free from device-related intervention	30 Days	Core Lab
Aortic Stent-Graft Effectiveness Measures			

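### The month-and-year date rule in SAP Section 4.7 has no floor at the procedure, so a missing-day adverse event in the procedure's own month is dated before treatment

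*Combined protocol and SAP*

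**What the plan says.** SAP Section 4.7 (Handling of Missing Dates) rules out date imputation for the primary analysis and permits it for adverse events if an analysis requires it. It then gives one principle and two rules.

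- Principle: "the earliest possible date will be used, given the information available".
- Month and year known: "If the month and year are provided, but the day is missing, then the first day of the month will be imputed". No condition is attached.
- Year only known: 1 January, "or the first day after procedure imputed if the first day of the year is prior to the procedure".

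Only the year-only rule mentions the procedure. No other visible part of the SAP supplies a floor for the month-and-year rule.

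Two descriptive outputs use a 30-day horizon. Table 3 defines access-related complications at 30 days as "An Adverse Event determined by Site to be related to vascular access". Section 2 lists, for the reduced profile VBX cohort, "Summary of AEs through 30-day follow-up including Type Ic and IIc Endoleaks". The schedule of events in Section 4.1 (Table 4) collects adverse events from screening onward.

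**The concern.** The two rules treat the same event differently, and in the wrong order. The year-only rule recognises that a mechanical earliest date can fall before treatment and corrects for it. The month-and-year rule, which starts from more information, makes no such correction. A programmer who codes the sentence as written will give some treatment-emergent events a pre-treatment onset date.

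At stake is the classification of events close to the procedure in descriptive safety tables: whether an event appears as before or after treatment, and its day of onset. No decision rule of the trial depends on it.

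**Working it through.** The plan gives no figure on this point, so there is nothing to reproduce. The check applies the Section 4.7 rules as written to every calendar combination. All results are conditional on the day being missing.

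**Example.** Procedure on 15 June, event on 20 June.
- Recorded as June: imputed 1 June, 14 days before the procedure and 19 days from the truth.
- Recorded by year only: 1 January precedes the procedure, so imputed 16 June, 4 days from the truth.

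**Procedure dates affected.** For a procedure on day d of a month and an event later in that month, imputed date minus procedure date is 1 − d. This is negative unless d = 1. A 365-day year has 12 firsts of the month, so 365 − 12 = 353 dates (96.7%) are affected.

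**Same-month event pairs.** Take every procedure date and every event date from the procedure to month end. A month of length L gives L(L+1)/2 pairs.
- Seven months of 31 days: 7 × 496 = 3,472
- Four months of 30 days: 4 × 465 = 1,860
- One month of 28 days: 406
- Total: 5,738

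Pairs with the procedure on the 1st number 365. The rest, 5,738 − 365 = 5,373 (93.6%), are dated before the procedure. This share largely restates that few procedures fall on the 1st.

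**How early.** Summing (d − 1) over the pairs in a month gives (L−1)L(L+1)/6, which is 4,960, 4,495 and 3,654 for L = 31, 30 and 28.
- Total: 7 × 4,960 + 4 × 4,495 + 3,654 = 56,354 days
- Mean over misdated pairs: 56,354 / 5,373 = 10.5 days before the procedure
- Without procedure-day events the mean is 10.2 days and the maximum 29. A gap of 30 days arises only for an event on the day of a procedure performed on the 31st.

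**Distance from the true date, same 5,738 pairs.** Mean absolute error is 19.6 days under the month-and-year rule, 9.0 days if the same events were recorded by year only, and 8.9 days with the floor proposed below. With that floor, no pair is dated before the procedure and none leaves its reported month.

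**Effect on a 30-day count.** Assumption: procedure dates uniform over 2019–2022 (1,461 days) and event days uniform.
- True events on days 0–30: 1,461 × 31 = 45,291. Of these, 21,520 (47.5%) are dated before the procedure under the current rule.
- True events on days 31–60: 1,461 × 30 = 43,830. Of these, 21,520 (49.1%) are pulled back into days 0–30. Events after day 60 cannot be, because the rule moves a date back by at most 30 days.
- Current rule, if negative days are excluded: 45,291 − 21,520 + 21,520 = 45,291. The two errors cancel.
- Current rule, if negative days are kept: 45,291 + 21,520 = 66,811.
- With the floor: 45,291 + 21,520 = 66,811, an overcount of 47.5% (21,520 / 45,291).

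So the floor changes a 30-day count only if programming drops events dated before the procedure. If events cluster early, the current losses exceed the gains and the cancellation fails.

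**The case against.** The best defence is that the general principle already covers the case. For an event known to follow a procedure on 15 June, 1 June is not a possible date, so "the earliest possible date will be used, given the information available" could be read as an implied floor. That reading is reasonable, and it makes this a small repair. It does not settle the matter, because the specific sentence gives the first of the month without condition while the next sentence spells out its own floor. Two competent programmers could code it differently.

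A second objection is that harm to the 30-day outputs is not shown. This stands. A reader might infer that post-procedure events would drop out of the 30-day access-complication and reduced profile VBX summaries. Neither Table 3 nor Section 2 states a lower bound at the procedure, and an event dated to day −14 still lies within a span running through day 30. Parts of the SAP are redacted, and the protocol section on adverse events that the SAP cites is not part of the text available here, so an exclusion can be neither shown nor ruled out.

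Third, under uniform timing the present rule's two errors offset in a 30-day count and the floor removes the offset. This also stands and is counted as a cost below.

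Fourth, because adverse events are collected from screening, a first-of-month date may sometimes be right. That is why the floor must not apply to events known to have begun before the procedure.

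**Conclusion.** The point holds as a minor inconsistency between two adjacent rules. Taken literally, the month-and-year rule gives a pre-treatment date to a post-procedure, missing-day event in the procedure's own month on 353 of 365 procedure dates, on average about 10 days early across misdated events. The less complete year-only date is handled better. The date arithmetic needs only the literal reading; the averages weight all calendar combinations equally.

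The reach is limited. Section 4.7 keeps imputation out of the primary analysis, so the co-primary tests, their error rate and their power do not change. The documents do not say how many partial dates to expect, and there may be none. Only descriptive outputs that use onset relative to the procedure are exposed, and 30-day counts move only under an exclusion that no visible text states.

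A reader might also infer that Section 4.7 is defective for not saying whether a stage or index procedure is the reference, or how subjects who receive CTAG but not TAMBE are handled. The documents do not support making that part of this point. Table 5 places the procedure at day 0, Section 4.2 counts visits from the date of treatment, and Section 3.1 concerns how long CTAG-only subjects' events are reported. At most that is missing detail, not a rule giving a wrong date.

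**What to change.** Add to the month-and-year rule in Section 4.7: *or, if the reported month is the month of the procedure and the event is not known to have started before the procedure, the first day after the procedure (the procedure date if the following day falls in the next month).* The bracketed part is needed because a plain day-after floor would put events outside their reported month for procedures on the 12 month-end dates.

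The cost is one clause in the SAP and one conditional line of code. There are three downsides:

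- A missing-day event on the procedure day is dated one day late on 353 of 365 procedure dates (all but the 12 month ends), much as the year-only floor already does.
- An event that began earlier in the procedure's month, but is not known to have done so, is dated after the procedure.
- The first-of-month rule still pulls some day 31–60 events into days 0–30. Where the two errors previously offset, 30-day counts of missing-day events become conservative: 66,811 against a true 45,291 under uniform event days. Any 30-day table that uses imputed dates should state how many were imputed.
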